Statistical Analysis Plan

Post Exposure Prophylaxis for Leprosy in the Comoros and Madagascar

PEOPLE

Date: 24 September 2020

Author: [name]
Biostatistician, Institute of Tropical Medicine, Antwerp, Belgium

Approved by: Coordinating Investigator
[name]

Date: 24 / 09 / 2020

Table of Contents

1. Introduction.....	2
2. Study design and objectives.....	2
2.1. Study design	2
2.2. Study objectives	3
3. Deviations from protocol	3
4. Description of study population.....	4
4.1. Patient accounting	4
4.2. Description of study population	4
5. Description of efficacy patient populations and outcomes	4
5.1. Patient populations	4
5.1.1. Intention to treat (ITT) analysis	4
5.1.2. Per protocol (PP) analysis.....	5
5.2. Efficacy study endpoints	5
6. Interim analysis.....	6
7. Analysis of main efficacy outcomes: incidence rate of leprosy	6
7.1. Subgroup analyses.....	6
7.2. Other aspects	6
a. Multiplicity	6

b. Missing data	7
8. Analysis of secondary efficacy objectives	7
8.1. To assess cost and feasibility of SDDR-PEP under program conditions	7
8.2. To identify patterns of clustering in transmission of leprosy, allowing better targeting of control measures	7
8.3. To monitor rifampicin resistance among leprosy patients	8
9. Safety analyses	8
9.1. Safety analysis population	8
9.2. Safety outcomes and analyses	8
9.2.1. Adverse events	8

1. Introduction

This Statistical Analysis Plan (SAP) provides a detailed and comprehensive description of the main, pre-planned analyses for the study “Post Exposure Prophylaxis for Leprosy in the Comoros and Madagascar”, including interim analyses. The purpose of this study is to document effectiveness of three alternative ways of implementing post exposure prophylaxis (PEP) at village level, by comparing to villages in which no PEP is provided. The study conduct is described in the Protocol (Clinicaltrials.Gov. NCT03662022).

These planned analyses will be performed by the statistician(s) at the Clinical Trials Unit of the Institute of Tropical Medicine (Antwerp) and the research consortium. The analysis results will be described in a statistical analysis report, to be used as the basis of the primary research publications. This document describes statistical methods for the primary and secondary objectives of the study as defined by protocol. Additional analyses may be performed but are not covered by the current analysis plan.

Two interim analyses will be conducted upon completing the second and third door-to-door surveys in which incidence rates of leprosy to date in study arms 2, 3 and 4 will be compared to the incidence rate in arm 1, just as in the final analysis. These interim analyses will allow us to assess whether the a priori assumptions on annual incidence made have been realistic or whether an extended study duration should be considered.

This analysis plan should be finalized and approved before the first interim analysis that will be performed by the study statistician. Major changes in statistical methodology used for the main and pre-planned analyses from this SAP, will require detailed description and justification in the statistical analysis report. The final analysis datasets, programs, and outputs are archived following good clinical practice guidelines (ICH E9).

2. Study design and objectives

2.1. Study design

The PEOPLE study is a cluster randomized trial. There will be four door-to-door surveys of which the first one will allow us to calculate a baseline leprosy prevalence

per island. On the Comoros villages have been randomized after having been grouped by island into 'Blocks' of four in decreasing order of incidence over the period 2013-2017. Within each block villages were randomly and mutually exclusively allocated to the four study arms. For the study district in Madagascar reliable incidence estimates were not available. For that reason randomization for Madagascar is foreseen only for the end of the first study year, once the first screening round has been completed.

There will be four study arms to which villages on Madagascar and the Comoros islands Anjouan and Mohéli will be randomly allocated. These villages have been preselected based on reported leprosy incidence over the period 2013-2017. In all four study arms, annual door-to-door surveys will be conducted covering entire villages. All permanent residents will be invited for screening for leprosy. Leprosy patients (further referred to as 'index patients') detected will be offered free treatment according to the international and country guidelines. Depending on the study arm, contacts of leprosy patients will be offered PEP. In arm 1 no PEP will be provided, which is the current routine care on Madagascar and the Comoros. In arms 2, 3 and 4 a single dose of 20 mg per kg bodyweight of Rifampicin (hereafter called 'SDDR-PEP') will be offered to all eligible participants who have not received Rifampicin in the preceding 2-year period. In arm 2 only household contacts of an index patient will be provided with SDDR-PEP, which target group is considered the standard approach when PEP is provided for leprosy. In arms 3 and 4 SDDR-PEP will also be provided to neighbourhood contacts living within a radius of 100 meter of an index patient. In arm 3 all such contacts (including household contacts) will be provided SDDR-PEP, in arm 4 SDDR-PEP will be provided to all household contacts and to all those within the 100-meter perimeter testing positive to a serological screening test. If in arms 3 or 4 more than 50% (arm 3) or 75% (arm 4) of the population live within 100 meters of an index case, the entire village will in principle be eligible for PEP.

2.2. Study objectives

Primary objective:

To compare effectiveness in curbing transmission of leprosy of three different approaches of post exposure prophylaxis

Secondary objectives:

1. To assess cost and feasibility of SDDR-PEP under program conditions
2. To identify patterns of clustering in transmission of leprosy, allowing better targeting of control measures
3. To monitor rifampicin resistance among leprosy patients
4. To estimate incidence and prevalence of smear positive pulmonary tuberculosis in the study villages

3. Deviations from protocol

In the protocol one of the secondary objectives was to estimate incidence and prevalence of smear positive pulmonary tuberculosis (see section above). The criterion to collect sputum was reported cough of 2 weeks duration or more. On a total population screened of just over 102,000 during the first year, only 115 (0.11%) reported such

cough. Either the question is not properly understood or cough is not a good screening criterion in the context of this study population. It was therefore decided to drop this secondary objective.

4. Description of study population

The study population will be described overall, and in each island (Anjouan, Mohéli, Madagascar) separately.

4.1. Patient accounting

Details of subjects screened, those who meet the study inclusion criteria, those who are eligible and enrolled, those who are eligible but not enrolled, those who withdraw from the study after randomization and those who are lost to follow-up will be summarized in a CONSORT flow diagram. The number of participants attending each annual survey will be reported. Since people were informed about their assigned study arm before providing consent and enrollment, the proportion of eligible subjects who are not enrolled will also be summarized by study arm.

4.2. Description of study population

Participants in each study arm, overall and by island, will be described with respect to baseline characteristics (i.e. at time of randomization). The description will be in terms of medians and quartiles for continuous characteristics and using counts and percentages for categorical characteristics. The clinical importance of any imbalance will be noted but statistical tests of significance of baseline imbalance will not be undertaken.

5. Description of efficacy patient populations and outcomes

5.1. Patient populations

Note that in Madagascar enrolment/randomization will only take place at the second survey. Hence for Madagascar only data from the second survey onwards will be used for the primary objective. For secondary objectives 2 and 3 data from the first survey will also be used.

We will analyse the efficacy data using Intention-to-Treat and Per-Protocol approaches, with Intention-to-Treat as primary approach.

5.1.1. Intention to treat (ITT) analysis

In the Intention-to-Treat analysis, all participants will be analysed according to their randomized allocation, even in case they do not receive SDDR-PEP as allocated, show protocol violations prior to or during the study.

5.1.2. *Per protocol (PP) analysis*

In the per-protocol analysis only participants who receive SDDR-PEP as planned, have complete follow-up, and follow the protocol as planned are included.

In Table 1 the protocol violations are classified as minor and major where minor violations can be included in the PP analysis population and major violations are excluded.

Table 1: The protocol violations classified as minor or major violation

Protocol Violation	Major/Minor Violation	Comments
Inclusion criteria		
1. Living in one of the study villages	Major	
2. Ages 2 years and above (only applicable for those receiving SDDR-PEP)	Major	
3. Able and willing to provide informed consent for leprosy and tuberculosis screening, and SDDR-PEP administration	Major	
4. For leprosy index cases only: able and willing to provide informed consent for participation and sampling	Major	
Exclusion criteria (only applicable for those receiving SDDR-PEP)		
1. Signs of active leprosy	Major	
2. Signs of active pulmonary tuberculosis	Major	
3. Having received Rifampicin within the last 24 months	Major	
Treatment violations		
1. Missing SDDR-PEP	Major	
2. Not following the randomized intervention	Major	
Follow-up violations		
1. Incomplete follow-up	Minor	

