8.1. To assess cost and feasibility of SDDR-PEP under program conditions

Costs will be calculated per person screened, per person treated with SDDR-PEP and per leprosy case averted.

8.2. To identify patterns of clustering in transmission of leprosy, allowing better targeting of control measures

Results of DNA finger printing will be used to assess the degree of clustering at household and at village level. We will calculate proportions of patients belonging to a same cluster by household and by village. The space-time K-function will be used to assess clustering in time and space, to be triangulated with results of DNA finger printing. For this purpose, we will use results of all leprosy patients identified, including those found at baseline.

To establish the transmission networks in the Comoros islands and in the study area in Madagascar, we will overlay the molecular network with the spatial- and social networks. This will determine whether the 100m high risk zones around each index patient, applied in this study, capture most transmission events, or whether additional risk factors, beyond spatial, need to be taken into account in future PEP administration efforts in the study areas and elsewhere. Phylogenetic clustering of the *M. leprae* isolates allows us to identify risk factors for leprosy due to recent transmission. The findings of the spatial and social network analysis can be mapped onto a phylogenetic tree and molecular clusters based on the VNTRs, which can reveal risk factors for transmission of leprosy.

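### The per-protocol rule can drop undosed PEP targets only in arms 2-4, so the per-protocol rate ratio against arm 1 can move below 1 without a PEP effect

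*SAP*

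**What the plan says.** SAP Section 5.1 names two efficacy approaches, with ITT as primary. Section 5.1.2 defines the other: "In the per-protocol analysis only participants who receive SDDR-PEP as planned, have complete follow-up, and follow the protocol as planned are included". It adds that "minor violations can be included in the PP analysis population and major violations are excluded". Under treatment violations, Table 1 lists "Missing SDDR-PEP" and classes it as Major.

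Section 2.1 sets out who is meant to be dosed:

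- Arm 1: "In arm 1 no PEP will be provided".
- Arm 2: "In arm 2 only household contacts of an index patient will be provided with SDDR-PEP".
- Arm 3: everyone within 100 m of an index patient; "In arm 3 all such contacts (including household contacts) will be provided SDDR-PEP".
- Arm 4: household contacts, plus people within 100 m who are seropositive.

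The same section opens PEP in principle to the whole village when more than 50% (arm 3) or 75% (arm 4) of the population live within 100 m of a case.

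The Section 7 model has study arm as its only fixed effect, with island, block and village as nested random effects. Section 8.2 speaks of "100m high risk zones around each index patient" and defines six contact categories: same household, four distance bands up to 100 m, and 100 m or beyond.

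**The concern.** A missed dose presupposes a planned dose. The exclusion therefore acts on targeted people in arms 2-4 and has no counterpart in arm 1, where people in the same position relative to an index patient all stay in. If the people removed have more leprosy than the average resident, the intervention side of the comparison loses risk for a reason unrelated to the drug. The random effects cannot correct this, because the change is in the mix of people within a village.

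What is at stake is how per protocol is read beside ITT. A stronger per-protocol ratio would naturally be taken to show that PEP works in those who take it, yet the exclusion rule can produce that pattern by itself, and more so as coverage worsens. In addition, villages were randomised and the objective is to curb transmission, so undosed residents belong to the effect being measured.

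**Working it through.** The SAP gives no per-protocol figure, contact share, relative risk or coverage, so there is no stated result to reproduce. Every input below is an assumption.

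**Reading used.** Non-targeted residents and all of arm 1 have no planned dose and are kept. Undosed targeted people in arms 2-4 are dropped.

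**Formula with no PEP effect and equal follow-up.** Let f be the share of residents who are targeted contacts, R their risk relative to other residents, and m the share of contacts undosed. Dosed and undosed contacts have the same risk.

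- Arm 1 mean risk: fR + (1 - f)
- Per-protocol mean risk in a PEP arm: [f(1 - m)R + (1 - f)] / (1 - fm)
- Null per-protocol ratio: the second divided by the first

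**Arm 3, village not above the 50% threshold.** Example with f = 0.4, R = 3, m = 0.3: the arm 1 mean is 1.2 + 0.6 = 1.8. The per-protocol mean is (0.84 + 0.6)/0.88 = 1.636. The ratio is 1.636/1.8 = 0.909.

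| f | R | m = 0.1 | m = 0.2 | m = 0.3 |
|---|---|---|---|---|
| 0.4 | 2 | 0.982 | 0.963 | 0.942 |
| 0.4 | 3 | 0.972 | 0.942 | 0.909 |
| 0.5 | 2 | 0.982 | 0.963 | 0.941 |
| 0.5 | 3 | 0.974 | 0.944 | 0.912 |

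**Smaller target group, as is likely in arm 2.** With R = 2 and m = 0.2, f = 0.05 gives 0.991 and f = 0.1 gives 0.983.

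**Simulation check.** With 4 million people per arm, no PEP effect, f = 0.3, R = 3 and m = 0.2, the per-protocol ratio was 0.938 and the ITT ratio in the same run 0.995. Their quotient, 0.938/0.995 = 0.943, agrees with the formula's 0.944.

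**Whole village eligible.** With f = 1, both means equal R and the ratio is exactly 1, provided uptake is unrelated to risk.

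**Undosed contacts with a different risk.** Take f = 0.3, dosed R = 2, m = 0.2. The retained mean is (0.48 + 0.7)/0.94 = 1.255. The ratio falls below 1 only if the undosed contacts' relative risk exceeds that value. A relative risk of 1 gives 1.255/1.24 = 1.012, 1.5 gives 0.988, and 3 gives 1.255/1.36 = 0.923.

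**The case against.** - **ITT is primary.** It keeps undosed people and already carries the village-level effect, and the SAP attaches no decision to per protocol. This stands and limits the weight of the point.
- **The direction is not guaranteed.** The SAP's high-risk wording is a working premise. The same section sets out to test whether the zones capture most transmission and whether distance predicts incidence. No risk is given for missed contacts, and the last calculation shows that the sign can flip. This stands, so the direction has to be stated as conditional.
- **The densest villages escape.** Above the whole-village thresholds the mechanism disappears if uptake is unrelated to risk. This stands, and is why the arm 3 range stops at a 50% contact share.
- **Refusers may never enrol.** Table 1 lists willingness to consent to SDDR-PEP as an inclusion criterion, and Section 4.1 says people knew their arm before consenting. Those who decline at that stage would be outside ITT too. The undosed share that matters is among enrolled people, and the assumed 20-30% has no support in the SAP. However, Section 5.1.1 does foresee participants who are not dosed as allocated.
- **Another reading exists.** Taken literally, the Section 5.1.2 sentence keeps only dosed people. That would empty arm 1, so it cannot be intended.
- **Selection is a known limit of any per-protocol set.** True, but here the rule acts on one side only, by construction, and the data to reduce the imbalance are already planned.

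**Conclusion.** The one-sided exclusion follows directly from Sections 2.1 and 5.1.2 with Table 1, and nothing in the Section 7 model offsets it. If undosed contacts have above-average village risk, the per-protocol ratio against arm 1 is below 1 with no PEP effect: about 0.91-0.96 in arm 3 villages not above the threshold with 20-30% undosed, and 0.97-0.98 with 10%. These figures rest on a contact share of 40-50%, a contact relative risk of 2-3, and equal risk in dosed and undosed contacts.

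A reader might infer that the per-protocol result must favour PEP in every arm even if PEP is inert, or that arm 4 is worst because untreated seropositives are removed. The documents support neither. The shift depends on the risk of the undosed, disappears under whole-village eligibility with uptake unrelated to risk, and can reverse. The SAP gives no risk for seropositives, and the group targeted in arm 4 is narrower than in arm 3. The point concerns a non-primary analysis and should be corrected before that analysis is run; the primary result is not in question.

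**What to change.** Amend Section 5.1.2 and Table 1 in one of two ways:

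1. **Keep the individual-level set but adjust it.** Add contact category as a fixed effect in the per-protocol model, using household and the Section 8.2 distance bands to the nearest index patient. Define it at the enrolment survey and identically in all four arms, including arm 1. Section 2.1 has annual surveys in every arm, so index patients are identified in arm 1 as well.
2. **Remove the one-sided exclusion.** Keep all enrolled residents, dosed or not, and delete the missed dose as an individual violation. Make clear that the separate Table 1 item on not following the randomised intervention does not bring it back.

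In either case, state what per-protocol status means for arm 1 and for non-contacts, label the analysis as supportive, and say that a per-protocol effect stronger than ITT is not evidence of efficacy when PEP is taken.

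The cost is SAP wording and a modest rerun with no new data collection. Section 8.2 builds its categories on 2019 index cases, so they must also be derived at the second survey for Madagascar, where enrolment takes place. Option 1 leaves residual selection by serology and uptake, and a category fixed at enrolment misses contacts of index patients found later. Option 2 brings per protocol close to ITT.

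A village coverage cut-off should not be the main remedy: it would drop villages only from arms 2-4 and repeat the asymmetry at cluster level.

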5.2. Efficacy study endpoints

Primary endpoint

The primary efficacy objective is to compare leprosy incidence rate. The health worker will perform a physical examination to look for signs of leprosy. Note that for this study, the diagnosis of leprosy will be made based on the so-called cardinal signs, i.e. a patch with loss of sensation, enlarged peripheral nerves and/or a slit skin smear positive for

acid fact bacilli. Results of qPCR and anti-PGLI testing will be not be used as diagnostic criteria.

Secondary endpoints

Genotyping will be done by a novel sequencing technique called the Deeplex® MycLep assay.

Rifampicin resistance will be tested with molecular markers.

6. Interim analysis

Two interim analyses will be conducted upon completing the second and third door-to-door surveys in which leprosy incidence rates to date in study arms 2, 3 and 4 will be compared to the leprosy incidence rate in arm 1, just as in the final analysis. These interim analyses will allow us to assess whether the a priori assumptions on annual incidence made have been realistic or whether an extended study duration should be considered.

The analysis performed will be similar to the analysis of the main efficacy outcome (Section 7) but restricted to data up to the second resp. third survey. Hence the interim analysis after completing the second survey will only include data from the Comoros.

7. Analysis of main efficacy outcomes: incidence rate of leprosy

Each diagnosis of leprosy made after the survey in which the participant was enrolled will be counted as an incident case. Note that not only diagnoses made at the annual surveys but also diagnoses made in between the surveys will be counted. For each individual we will calculate the exact time at risk. For individuals residing in intervention villages (arms 2, 3 and 4) we will use the number of days from the median date of the first SDDR-PEP administration in the village until end of follow-up or until diagnosis of leprosy.

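### As written, Table 1 can remove incident cases who decline sampling from the per-protocol set, an exclusion that non-cases can never meet

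*SAP*

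**What the plan says.** Section 5.1 of the SAP sets two efficacy analyses: "We will analyse the efficacy data using Intention-to-Treat and Per-Protocol approaches, with Intention-to-Treat as primary approach". Section 5.1.2 forms the PP set from Table 1, under the rule that "minor violations can be included in the PP analysis population and major violations are excluded".

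The fourth inclusion criterion in that table reads "For leprosy index cases only: able and willing to provide informed consent for participation and sampling". It is classed Major, and nothing stands against it in the Comments column.

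Three other places decide whom it reaches:

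- Section 2.1, in the paragraph on annual surveys in all four arms: "Leprosy patients (further referred to as 'index patients') detected will be offered free treatment". The same section later writes index case for the same people.
- Section 7 defines the primary event: "Each diagnosis of leprosy made after the survey in which the participant was enrolled will be counted as an incident case".
- Section 5.2 states how a case is recognised: "the diagnosis of leprosy will be made based on the so-called cardinal signs". These are an anaesthetic patch, enlarged peripheral nerves and/or a positive slit skin smear. It adds: "Results of qPCR and anti-PGLI testing will be not be used as diagnostic criteria".

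**The concern.** Membership of an analysis set should not depend on something that can happen only after the outcome has occurred. If index patient includes everyone detected at any survey, criterion 4 first applies to an enrolled resident when that resident becomes a case. Refusal then deletes an event from the PP analysis, and no comparable refusal can delete a non-case.

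Two things are at stake. The PP incidence rate would be too low by the share of cases who decline. The PP rate ratio would also be distorted wherever that share differs between a PEP arm and arm 1. A difference is possible because arms are known: Section 4.1 opens a sentence with "Since people were informed about their assigned study arm before providing consent and enrollment". A PP result that departs from the ITT result could then be read as an effect of receiving PEP as planned when it partly reflects who agreed to be sampled.

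**Working it through.** The SAP gives no refusal rate or PP figure, so there is nothing of its own to reproduce. The check has two parts.

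**Tracing the text**

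1. A resident without leprosy is enrolled and satisfies criteria 1 to 3.
2. At a later survey, or between surveys, the resident is diagnosed. Under Section 7 this is an incident case.
3. Under Section 2.1 the person is now a leprosy patient detected, hence an index patient.
4. Criterion 4 applies to index cases. If the person declines sampling, the criterion is not met.
5. Table 1 classes this as Major, and Section 5.1.2 excludes Major violations. The event is lost to the PP analysis.
6. A resident who stays free of leprosy never reaches step 3.

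Exclusion therefore needs both leprosy and refusal. It is conditional on the outcome, not automatic.

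**Size**

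Let s_1 and s_PEP be the shares of incident cases who decline sampling in arm 1 and in a PEP arm. At low incidence the person-time of the removed cases is negligible, so:

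- PP rate ≈ true rate × (1 − s)
- PP IRR ≈ true IRR × (1 − s_PEP)/(1 − s_1)

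All shares below are assumptions.

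| s_1 | s_PEP | Factor | PP IRR if true IRR = 1.00 | PP IRR if true IRR = 0.70 |
|---|---|---|---|---|
| 10% | 10% | 0.90/0.90 = 1.00 | 1.00 | 0.70 |
| 5% | 10% | 0.90/0.95 = 0.947 | 0.95 | 0.66 |
| 10% | 5% | 0.95/0.90 = 1.056 | 1.06 | 0.74 |
| 10% | 20% | 0.80/0.90 = 0.889 | 0.89 | 0.62 |
| 0% | 20% | 0.80/1.00 = 0.80 | 0.80 | 0.56 |
| 20% | 0% | 1.00/0.80 = 1.25 | 1.25 | 0.875 |

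Person-time check, with assumed values of 10,000 people per arm, 60 cases, 3 years, and cases contributing half the time on average:

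- No refusal: 60 / (9,940 × 3 + 60 × 1.5) = 60/29,910 = 0.002006 per year.
- 20% refusal: 48 / (9,940 × 3 + 48 × 1.5) = 48/29,892 = 0.001606 per year.
- Ratio: 0.8005, against 0.80 from the approximation.

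Equal refusal leaves the IRR alone and lowers each arm's PP rate by about the refused share. Unequal refusal moves the IRR, and the direction depends on which arm refuses more.

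**The case against.** **Criterion 4 may be an entry condition only.** It sits under the inclusion criteria, and a person validly enrolled without leprosy does not ordinarily breach an inclusion criterion by falling ill later. Section 8.2 also contrasts index cases from 2019 with incident cases in 2020. This reading is possible, but the SAP does not state it. Table 1 carries no such limit, and the year attached in 8.2 suggests that index cases are not confined to one survey. On the entry-only reading the row has no use in an efficacy PP set, because someone already diagnosed at the enrolment survey is not an incident case under Section 7. The row is therefore either harmful or idle, and the same change suits both readings.

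**Refusal may not differ by arm.** This stands. Section 4.1 shows only that arms were known before consent, and Section 2.1 offers detected patients free treatment in every arm. Differential refusal is plausible but not shown. With equal refusal the IRR, which is the outcome Section 7 says will be reported, does not change.

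**Sampling may be part of diagnosis.** This stands in part. A reader might infer from the sentence on qPCR and anti-PGLI that samples serve only genotyping and resistance testing. Section 5.2 does not support that, because a positive slit skin smear is one of the diagnostic signs and the SAP does not define what sampling covers. A case diagnosed on a patch or enlarged nerves nevertheless remains a valid event without any sample.

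**Only a supporting analysis is affected.** This stands. Section 5.1.1 keeps participants with violations before or during the study in the ITT analysis.

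**Conclusion.** The point holds for the PP analysis, on the plain wording of Sections 2.1, 5.1.2 and 7. PP membership can turn on a refusal that only people with the outcome are able to make, and the resulting exclusion removes events and no non-cases.

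The understatement of the PP rate equals, to a close approximation, the share of cases who decline. Bias in the PP IRR requires that share to differ by arm. With assumed shares between 0% and 20% the factor lies between 0.80 and 1.25, and 10% against 20% gives 0.89. These sizes illustrate the mechanism and are not estimates for this trial.

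A reader might infer two stronger statements, and the SAP supports neither. One is that participants leave the PP set simply because they develop leprosy; they must also decline consent. The other is that the trial's main result is biased; ITT is primary and is untouched.

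**What to change.** In Table 1, take criterion 4 off the list of Major violations for the efficacy PP set, or add a comment that it does not apply to cases diagnosed after enrolment. In Section 5.1.2, state two things:

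- Criterion 4 governs only inclusion in the sample-based analyses, namely genotyping in 8.2 and rifampicin resistance in 8.3. The model in 8.3 is already limited to patients with a test result, so that analysis loses nothing.
- The PP analysis counts every incident case that meets the diagnostic criteria of Section 5.2 in a participant who consented to screening under criterion 3, whether or not further samples were given.

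The cost is one table row and a sentence or two, with no new data. The change should be made before results by arm are seen. It removes this source of distortion (factor 1.00 in every arm). It does not recover cases that could have been diagnosed only from a smear that was declined, since the slit skin smear remains one of the diagnostic signs.

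### The per-protocol set can drop a later-diagnosed leprosy case for signs judged present at dosing, but only among PEP recipients, so any such removal lowers the rate in PEP arms and never in arm 1

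*SAP*

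**What the plan says.** - **PP exclusions (SAP Section 5.1.2, Table 1).** One block of the table is headed "Exclusion criteria (only applicable for those receiving SDDR-PEP". Its first row is "Signs of active leprosy", graded major. The text above the table gives the consequence: "minor violations can be included in the PP analysis population and major violations are excluded".
- **Who receives PEP (Section 2.1).** The control arm receives none: "In arm 1 no PEP will be provided". Recipients differ between the other arms. "In arm 2 only household contacts of an index patient will be provided with SDDR-PEP", whereas arm 3 extends PEP to everyone within 100 metres, and "in arm 4 SDDR-PEP will be provided to all household contacts and to all those within the 100-meter perimeter testing positive" on serology. In arms 3 and 4 whole villages become eligible once a stated share of residents lives that close to a case.
- **Counting rule (Section 7).** "Each diagnosis of leprosy made after the survey in which the participant was enrolled will be counted as an incident case". This applies to all arms, and there is no separate rule for disease that was already present but not recognised.
- **Status of the analyses (Section 5.1).** Efficacy is analysed both ways, "with Intention-to-Treat as primary approach". Section 5.1.1 keeps protocol violators in the intention-to-treat (ITT) set.

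**The concern.** The excluding condition is close to the endpoint itself: Section 5.2 bases the diagnosis of leprosy on clinical signs, and Table 1 excludes for signs of leprosy. An exclusion so near the outcome should act equally in all arms, or it will move the comparison by definition alone. Here it cannot act in arm 1, because nobody there receives PEP.

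At stake is what the PP result can be taken to show. A PP rate ratio further below 1 than the ITT one would normally be read as the effect of PEP when delivered as intended. Part of that gap could instead come from deleting events in one set of arms. The SAP also does not say whether signs are judged from the record at dosing or in retrospect after a diagnosis. A retrospective judgement would be made with the outcome, and usually the arm, already known.

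**Working it through.** **Step 1: follow one person through the rules.** Take someone not diagnosed at the enrolment survey, diagnosed later, and judged to have had signs at the time when PEP was given in the village.

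| Person | Incident case under Section 7? | Can the active-leprosy row apply? | In the PP analysis |
|---|---|---|---|
| Arm 1 | Yes | No, no PEP given | Person and event stay |
| Arms 2–4, no PEP received | Yes | No, not a recipient | This row leaves person and event in |
| Arms 2–4, PEP received, signs classed as a violation | Yes | Yes | Person and event removed |
| Arms 2–4, PEP received, signs never classed | Yes | No violation on record | Person and event stay |

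Only the third line differs from arm 1, and it exists only in PEP arms.

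**Step 2: direction.** Section 7 uses arm 1 as the reference, so a rate ratio below 1 favours PEP. Removing events from the numerator of a PEP arm can only lower the ratio. The person-time lost with them is trivial. Section 3 reports just over 102,000 people screened in year one; split evenly over four arms (an assumption) that is about 102,000 / 4 = 25,500 per arm, and 6 people are 6 / 25,500 = 0.02%.

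**Step 3: size.** The SAP gives no expected case count, missed-case rate or PEP coverage, so there is no figure of the plan's own to reproduce. Everything below is assumed, with no true effect and equal person-time.

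With n cases expected per arm and k removed, the PP rate ratio is (n − k)/n:
- n = 60: k = 2 gives 58/60 = 0.97; k = 4 gives 56/60 = 0.93; k = 6 gives 54/60 = 0.90.
- n = 40: k = 6 gives 34/40 = 0.85.

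To show what drives k, write k/n = f × r × a. Here f is the share of counted cases whose disease was already present but overlooked, r is the share of those who received PEP, and a is the share of those later classed as violations. The PP rate ratio is then 1 − f × r × a:

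| f | r | a | PP rate ratio with no true effect |
|---|---|---|---|
| any | any | 0 | 1.00 |
| 0.1 | 0.1 | 1 | 0.99 |
| 0.2 | 0.5 | 0.5 | 0.95 |
| 0.2 | 0.5 | 1 | 0.90 |
| 0.3 | 0.8 | 1 | 0.76 |
| 0.5 | 0.8 | 1 | 0.60 |

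**Step 4: variation between PEP arms.** For fixed f and a, the distortion grows with r. Within any given village, those eligible under the arm 2 rule are a subset of those eligible under the arm 3 or arm 4 rule. The shift therefore need not be equal across the three comparisons with arm 1.

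**The case against.** **Removal is not automatic.** A reader might infer that leprosy overlooked at entry is always deleted in the PEP arms. The SAP does not support that. Signs that were truly overlooked are not on record, so Table 1 has nothing to act on and the case counts as it would in arm 1. Deletion needs recorded signs without a diagnosis, or a later ruling that signs were present at dosing, and the SAP describes no such look-back. This stands in full and is why the point is worded with *can*. It does not remove the point, because the SAP does not rule the look-back out either.

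**Only recipients are reached.** It would be wrong to treat arms 2 to 4 as affected throughout. Under this row, non-recipients there are handled exactly as in arm 1. This also stands.

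**The PP analysis is not primary.** Nor does the SAP attach a decision rule to it. A reader who concluded that the main result is biased would be mistaken, since the ITT set removes nobody for violations. The PP analysis is still one of two prespecified efficacy analyses, so a one-sided, outcome-related exclusion in it deserves correction.

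**Excluding people dosed against a criterion is what a PP set ordinarily does.** True, and harmless where the criterion is unrelated to the endpoint. Here the two nearly coincide.

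**The direction holds for this row only.** Other exclusions, such as the one for an omitted dose, also remove people, so nothing follows about the net bias of the PP analysis as a whole. This stands.

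**Conclusion.** The concern holds in limited form. In the PP analysis, the active-leprosy row can remove later-diagnosed cases among PEP recipients and can never do so in arm 1. Where it does, the PP rate falls in the PEP arms only, by more where more of the cases received PEP. Where no such violation is recorded, the effect is exactly nil.

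Its size cannot be derived from the SAP. The illustrative ratios, from 1.00 down to 0.60, show direction and what the size depends on. They are not estimates, and the lower values need large shares of overlooked disease, high coverage and complete reclassification, none of which the document supports. The primary ITT comparison is untouched. The point is worth correcting before analysis because it costs little and removes a judgement that could otherwise be made with the outcome known.

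**What to change.** For the efficacy PP set, change the active-leprosy row of Table 1 so that the violation is reported but does not exclude. Add one sentence to Section 5.1.2, for example: *A participant diagnosed with leprosy after the enrolment survey is not removed from the efficacy PP set, and the event is not discounted, because of signs judged present at dosing.* The row can still be listed and tabulated as a violation. No eligibility or dosing rule changes.

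The cost is one table row and one sentence. The downside is that a few people dosed against an eligibility criterion remain in the PP set.

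A heavier alternative is to drop early diagnoses in all four arms by one common rule, with person-time starting after the same window. That would also be symmetric, but it changes the case definition and time-at-risk rule in Section 7 and needs a window that the SAP does not supply. It is a trade-off for the sponsor and is not needed to settle this point.
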